**eGFR will be calculated with MDRD formula:**

$GFR (mL/min/1.73 m^2) = 175 \times (\text{Serum}_{\text{creatinine}})^{-1.154} \times (\text{Age})^{-0.203} \times (0.742 \text{ if female}) \times (1.212 \text{ if African American})$  (conventional units)

**2. Presence of hereditary (ATTRv) and wild-type (ATTRwt) ATTR**

ATTR patients with a ATTR gene sequencing with variant transthyretin will be considered as ATTRv.

ATTR patients with a ATTR gene sequencing with a result of « No Mutation » will be considered as ATTRwt.

**3. Presence of familial history of known cardiomyopathy (CM), polyneuropathy (PN), sudden cardiac death (SCD)**

Family history for each disease will be considered for 1st degree parent, siblings and 2nd/3rd grade family.

**4. Senso-motor Polyneuropathy**

Patients with at least one red flag in the neurological part of the ATTR-Amyloidosis red flags e-CRF part will be considered as patients with a senso-motor Polyneuropathy.

**5. Carpal Tunnel syndrome (CTS)**

Patients with a CTS will be patients with a bilateral or unilateral CTS.

Patients without CTS will be patients with a “NO” to the question “Carpal tunnel syndrome symptoms”

**6. Autonomic dysfunction**

Patients with autonomic dysfunction will be patients with at least one autonomic sign or autonomic symptom = “Yes”

**7. Cardiological manifestations**

Patients with cardiological signs will be defined as patients with at least one of the following criteria fulfilled:

Criterion	Value
In Cardiological assessments part of the e-CRF	
Atrial Fibrillation	Yes permanent
Pacemaker	Yes
AICD	Yes
In MRI part of the e-CRF	
LGE	Positive
In ECG part of the e-CRF	
Sinus rhythm	No
PR interval	< 80 ms or > 350 ms
QRS interval	< 60 ms or > 250 ms
Sokolow index	< 1 mm or > 70 mm
Pseudo-MI pattern	Yes
PPOr precordial R wave progression	Yes
LBBB	Ticked
RBBB	Ticked
Paced	Ticked
Intraventricular conduct delay	Ticked
LVOT	Yes
If longitudinal strain is done, strain apical preserved	Yes
LV end-diastolic diameter	< 20 mm or > 80 mm
MWT	< 15 mm or > 100 mm
MWT at septum	< 3 mm or > 50 mm
MWT posterior wall	< 3 mm or > 50 mm
LV mass index	< 40 g/m  or > 160 g/m 
Maximal aortic velocity	> 5 m/s
Mean gradient of Aortic valvular stenosis	> 70 mmHg
Area of Aortic valvular stenosis	< 0.2 cm  or > 3 cm 

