The diagnosis of amyloidosis is also obtained through biopsy of a clinically affected organ, with Congo red histology demonstrating pathognomonic green birefringence. However, when amyloidosis is suspected clinically, biopsy of subcutaneous fat, salivary gland, or rectum yields the diagnosis in 50% to 80% of patients with AL amyloidosis (*Ansari-Lari 2004, Gillmore 2016*). A much lower yield in patients with ATTR amyloidosis frequently results in a requirement for endomyocardial biopsy (EMB) to confirm the diagnosis (*Fine*

2014, Gillmore 2016). EMB is associated with a risk of complications, including myocardial perforation and tamponade that may be fatal and requires expertise that can introduce diagnostic delay (Maurer 2015, Gillmore 2016). ECGs are abnormal in 90% of cases with cardiac involvement (Mohty 2013). The low precordial and limb lead voltage is primarily due to the destruction and replacement of myocytes by the electrically inert amyloid. Although this pattern is exhibited by approximately 70% of AL-associated cardiac amyloidosis, only one third of patients with hereditary amyloidosis and wild-type amyloidosis show low voltage. The pseudoinfarction pattern as evidenced by QS waves in 2 consecutive leads is another common finding (Kapoor 2011). Differential diagnosis between HCM and cardiac amyloidosis is aided by measuring the ratio between QRS voltages and LV wall thickness (Elliott 2014).

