## 9.3. Variables

Variable	Data source(s)
Patient informed consent date	PATIENT INCLUSION
Patient visit date	PATIENT INCLUSION
Age ≥50 years	PATIENT INCLUSION
LVH Echo demonstrated end-diastolic LV MWT ≥15mm	PATIENT INCLUSION
Maximal end diastolic wall thickness	PATIENT INCLUSION
Sarcomeric HCM (Genetic testing)	PATIENT INCLUSION
Plasma cell dyscrasia	PATIENT INCLUSION
Fabry disease	PATIENT INCLUSION
AL, AA or any other amyloidosis	PATIENT INCLUSION
Severe aortic stenosis (defined as) Maximal aortic velocity >4 m/s or Mean gradient >40 mmHg	PATIENT INCLUSION
Birth date (mm-yyyy)	PATIENT INFORMATION
Gender	PATIENT INFORMATION
Weight	PATIENT INFORMATION
Height	PATIENT INFORMATION
Ethnic Origin	PATIENT INFORMATION
Date	CLINICAL EVALUATION
Diastolic blood pressure	CLINICAL EVALUATION
Systolic blood pressure	CLINICAL EVALUATION
Diagnosed hypertension	CLINICAL EVALUATION
Antihypertensive medication	CLINICAL EVALUATION
Coronary artery disease	CLINICAL EVALUATION
Renal insufficiency	CLINICAL EVALUATION
Diabetes Mellitus	CLINICAL EVALUATION
Lumbar spinal stenosis 1	CLINICAL EVALUATION
CTS – surgery history 2	CLINICAL EVALUATION
New York heart Association (NYHA) class	CLINICAL EVALUATION
Atrial Fibrillation (AF)	CLINICAL EVALUATION

Variable	Data source(s)
Pacemaker	CLINICAL EVALUATION
AICD (Automatic Implantable Cardiac Defibrillator)	CLINICAL EVALUATION
LGE (Late Gadolinium Enhancement)	CLINICAL EVALUATION
Heart rate	CLINICAL EVALUATION
Sinus rhythm	CLINICAL EVALUATION
PR Interval	CLINICAL EVALUATION
QRS interval	CLINICAL EVALUATION
Sokolow index	CLINICAL EVALUATION
Pseudo-MI pattern	CLINICAL EVALUATION
Poor precordial R wave progression	CLINICAL EVALUATION
LBBB RBBB Paced Intraventricular conduct delay	CLINICAL EVALUATION
Left Ventricular Ejection Fraction (LVEF)	CLINICAL EVALUATION
Left Ventricular Obstruction Tract (LVOT)	CLINICAL EVALUATION
Longitudinal strain done?	CLINICAL EVALUATION
LV end-diastolic diameter	CLINICAL EVALUATION
MWT	CLINICAL EVALUATION
MWT at septum	CLINICAL EVALUATION
MWT posterior wall	CLINICAL EVALUATION
Hypertrophic pattern Apical, Concentric, Asymmetric, Mix	CLINICAL EVALUATION
LV mass index	CLINICAL EVALUATION

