## 11 APPENDICES

### 11.1 APPENDIX 1: DATA DERIVATION DETAILS

Age = (Patient screening visit date – Birthdate + 1) /365.25 , where day of birth is imputed to 15, as only month and year of birth are recorded.

Diastolic Blood Pressure classes:

- < 60 mmHg,
- [61 – 70] mmHg,
- [71 – 80] mmHg,
- [81 – 90] mmHg,
- [91 – 100] mmHg,
- > 100 mmHg.

Heart Rate classes:

- < 50 bpm,
- [51 – 60] bpm,
- [61 – 70] bpm,
- [71 – 80] bpm,
- [81 – 90] bpm,
- [91 – 100] bpm,
- [101 – 120] bpm,
- > 120 bpm.

PR interval classes:

- [90 – 100] ms
- [101 – 110] ms
- [111 – 120] ms
- [121 – 130] ms
- [131 – 140] ms
- [141 – 150] ms
- [151 – 160] ms
- [161 – 170] ms
- [171 – 180] ms
- [181 – 190] ms
- [191 – 200] ms
- [201 – 210] ms
- [211 – 220] ms
- [221 – 230] ms

- [231 – 240] ms
- [241 – 250] ms
- [251 – 260] ms
- [261 – 270] ms
- [271 – 280] ms
- > 280 ms

Serum Free Light Chain Ratio:

sFLC Ratio = Kappa / Lambda,

sFLC ratio classes:

- < 0.26,
- [0.26 – 1.65],
- > 1.65.

Abnormal values for all quantitative variables will be defined after medical advise.

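### The PR, QRS and Sokolow limits in SAP 6.3 item 7 look like plausibility bounds, so low voltage and isolated PR prolongation can go uncounted as cardiological manifestations

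*SAP*

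**What the plan says.** SAP 6.3 item 7 defines a patient with cardiological signs as one with "at least one of the following criteria fulfilled". The list mixes yes/no items with numeric items. Three of the numeric items come from the ECG:

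- PR interval: "< 80 ms or > 350 ms"
- QRS interval: "< 60 ms or > 250 ms"
- Sokolow index: below 1 mm or above 70 mm

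The resulting prevalence is reported in FAS2, FAS3 and the ATTRv and ATTRwt subgroups (SAP 8.2). The same rule defines the cardiological symptomatology covariate (SAP 6.4), which is offered to the logistic regressions (SAP 8.1).

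Two other places bear on these limits. SAP Appendix 1 closes with the statement "Abnormal values for all quantitative variables will be defined after medical advise". Protocol section 7 describes low voltage as an ECG pattern of cardiac amyloid, seen in roughly 70% of AL cases, and adds that "only one third of patients with hereditary amyloidosis and wild-type amyloidosis show low voltage".

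**The concern.** An item in an any-one-of composite should separate patients who have the abnormality from those who do not. The three ECG limits are so wide that they seem suited to catching data-entry errors instead. If so, a patient whose only cardiac finding is low voltage or a moderately long PR interval is recorded as having no cardiological manifestation.

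The error in these three rows runs one way, because limits that are too wide can only lower the count. It reaches a reported secondary prevalence and a model covariate. SAP 6.3 also fixes values that Appendix 1 of the same document says are still to be defined, so a programmer has two incompatible instructions.

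**Working it through.** **1. The plan's own figures.** The documents give no figure for how many patients cross the ECG limits. The nearest stated figures are the precisions in Protocol 9.5, and both reproduce with 1.96 × √(p(1−p)/n):

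- Prevalence 10%, n = 1500: 1.96 × √(0.10 × 0.90 / 1500) = 1.52 points (stated 1.5).
- Sign frequency 30%, n = 1500 × 0.10 = 150: 1.96 × √(0.30 × 0.70 / 150) = 7.33 points (stated 7.3).

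**2. Are the limits plausibility bounds?** No passage gives their origin, so internal evidence has to serve.

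- *PR.* The classes in SAP Appendix 1 start at 90 ms and rise in 10 ms steps to 280 ms, with one open class above. The lower limit of 80 ms lies below every class. The upper limit of 350 ms lies 350 − 280 = 70 ms inside the open class.
- *Wall thickness.* The same table flags MWT "< 15 mm or > 100 mm", yet entry requires "LVH Echo demonstrated end-diastolic LV MWT ≥15mm" (Protocol 9.3). FAS1 contains only eligible patients, so the lower limit should never be met.
- *Aortic rows.* The row "Area of Aortic valvular stenosis" flags below 0.2 cm² (or above 3 cm²), although an area below 1.0 cm² is already an exclusion. The velocity and gradient rows flag above 5 m/s and 70 mmHg. Protocol 9.3 already calls above 4 m/s or 40 mmHg severe.
- *Contrast.* SAP 6.3 item 8 (laboratory signs) uses limits such as BNP above 100 pg/mL and troponin T above 14 pg/mL, which do act as abnormality limits.

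**3. Which findings lack another row?**

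| Finding | Other rows in item 7 that can count it |
|---|---|
| Conduction delay with wide QRS | LBBB, RBBB, intraventricular delay, paced, pacemaker |
| Low voltage | none; Sokolow is the only ECG voltage variable in Protocol 9.3 |
| Isolated PR prolongation | none |

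**4. Illustrative size for low voltage in ATTR.** Inputs are the 150 planned ATTR-CM patients (Protocol 9.5) and one third with low voltage (Protocol section 7). Two assumptions are added: none of these patients has a Sokolow index below 1 mm, and low voltage is independent of the other items.

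- Expected with low voltage: 150 / 3 = 50, or 33.3% (Wilson 95% CI 26.3 to 41.2%).
- Counted by the Sokolow row under the assumption: 0/150 (Wilson upper limit 2.5%).
- If the other items flag a share c, the composite loses (1 − c)/3.

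The documents do not give c, so a range is shown. The last column is 1.96 × √(c(1 − c)/150).

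| c | Composite with low voltage counted, 1 − (1 − c) × 2/3 | Loss, points | Sampling half-width at c, n = 150, points |
|---|---|---|---|
| 95% | 96.7% | 1.7 | 3.5 |
| 80% | 86.7% | 6.7 | 6.4 |
| 50% | 66.7% | 16.7 | 8.0 |

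The loss is below sampling error when the other items flag nearly everyone. It is about equal to sampling error at 80% and twice as large at 50%. No comparable figure can be given for PR prolongation, because the documents state no frequency for it.

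**The case against.** The case against has real weight.

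- *The protocol's emphasis.* A reader might infer that the protocol treats low voltage and conduction delay as typical of ATTR. It does not. It gives one third for low voltage in hereditary and wild-type disease, introduced by the word only, and it names conductive disorders for Val30Met disease.
- *Conduction delay.* A reader might infer that it goes uncounted. Five other rows can count it, so the QRS limit alone costs little.
- *What else can fire.* It is tempting to say that only the tick-box items and late gadolinium enhancement drive the composite. LV mass index above 160 g/m² is numeric and may be met in a population selected for thick walls.
- *PR classes.* Only the lower PR limit lies outside the tabulated classes. The upper one falls within the open top class.
- *Origin and tail probabilities.* The e-CRF is a separate document, so edit-check ranges cannot be confirmed. The chance of crossing the limits cannot be computed from the documents, since any mean and SD would be invented.
- *Independence.* The pseudo-MI and poor R-wave progression rows may overlap with low voltage, which would shrink the loss. The one-third figure also describes low precordial and limb-lead voltage, not a Sokolow threshold, so a revised Sokolow limit might not recover all of it.
- *Other reporting.* SAP 8.2 (Other analyses, item 3) already describes every CRF variable, and items 5 and 6 offer the CRF variables collected in both positive and negative patients to the regressions. PR, QRS and Sokolow are therefore not hidden. SAP section 4 calls all tests exploratory.

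These points narrow the concern without removing it. Separate description of an ECG variable does not correct a composite that leaves it out, and none of them reconciles SAP 6.3 with Appendix 1.

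**Conclusion.** The point holds in limited form. The three ECG limits appear to be plausibility bounds. This is an inference from the PR classes and the neighbouring rows, not something the documents state. The gaps that follow are low voltage and isolated PR prolongation; conduction delay is largely covered elsewhere.

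The cardiological manifestations prevalence can be understated, by an amount the documents do not allow one to fix. The illustration gives about 1.7 to 16.7 points in ATTR patients, with the other items flagging 95% down to 50%. It rests on independence, on no low-voltage patient reaching the Sokolow limit, and on the protocol's one-third figure. Overlap with other rows would make it smaller.

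The covariate carries the same misclassification. Its effect on the odds ratios cannot be signed, because no low-voltage frequency is given for scan-negative patients. The primary prevalence endpoint is unaffected.

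**What to change.** Reconcile SAP 6.3 item 7 with Appendix 1:

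1. Keep the present PR, QRS and Sokolow limits as data checks only.
2. In the endpoint and in the SAP 6.4 covariate, use the medically advised abnormal values that Appendix 1 already promises. Write them into item 7 and fix them before database lock. No cut-off is proposed here; that is a medical decision.
3. Apply the same check to the other numeric rows of the table (LV diameter, the wall-thickness rows, LV mass index and the aortic rows).

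Separate description of each ECG variable is already planned and needs no addition.

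The cost is SAP wording and a medical decision already foreseen, with no new data collection. The composite percentage may rise. If the interim analysis described in SAP section 3 used the present limits, its figure for this endpoint will not match the final one, and the final report should say so.

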## 2. Exclusion Criteria:

- a. Etiological diagnosis explaining the LVH prior to patient inclusion (eg, Sarcomeric HCM, Myeloma, Fabry disease, Sarcoidosis, any type of amyloidosis [AA, AL, TTR\*\*]).
- b. Severe aortic stenosis defined as aortic valve area (AVA) <1.0 cm^2.

*\*\* TTR diagnosis at exclusion criteria: Direct relative (siblings or parents) of a carrier with a known hereditary mutation in the TTR gene or any patient already diagnosed by any of the following: cardiac fixation at the bone scintigraphy, TR mutation at the genetic testing, biopsy with amyloidosis (positive red congo) and positive TTR staining.*

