#### 1. Inclusion criteria:

- a. Patient signed inform consent.
- b. Males and Females.
- c. Age  $\geq 50$  years.
- d. Left ventricular hypertrophy (LVH) defined as end-diastolic LV maximum wall thickness (MWT)  $\geq 15$ mm in Echocardiogram.

- e. *Plan to undergo or recently underwent radionuclide bone scintigraphy and/or SPECT with any of the following radio labelled tracers:  $^{99m}\text{Tc}$ -DPD or  $^{99m}\text{Tc}$ -PYP or  $^{99m}\text{Tc}$ -HMDP.*

*Scintigraphy will be defined at each site according to the standard grading:*

*Grade 0 = absent cardiac uptake*

*Grade 1 = mild uptake less than bone*

*Grade 2 = moderate uptake equal to bone*

*Grade 3 = high uptake greater than bone*

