## 2. Exclusion criteria

- a. *Etiological diagnosis explaining the LVH prior to patient inclusion (eg, Sarcomeric HCM, Myeloma, Fabry disease, Sarcoidosis, any type of amyloidosis [AA, AL, TTR\*\*])*

*\*\* TTR diagnosis at exclusion criteria: Direct relative (siblings or parents) of a carrier with a known hereditary mutation in the TTR gene or any patient already diagnosed by any of the following: cardiac fixation at the bone scintigraphy, TR mutation at the genetic testing, biopsy with amyloidosis (positive red congo) and positive TTR staining.*

- b. *Severe aortic stenosis defined as aortic valve area (AVA) < 1.0 cm^2*

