## 5 ANALYSIS SETS/POPULATIONS

### 5.1 FULL ANALYSIS SET

#### **Full Analysis Set 1 – Primary population**

Full Analysis Set 1 (FAS1) includes all patients who meet eligibility (inclusion/exclusion) criteria and with a radionuclide bone scintigraphy and/or SPECT performed with 99mTc-DPD/99mTc-PYP/99mTc-HMDP.

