### **6.4 COVARIATES**

- Grade (0, 1, 2, 3) and for grade 2&3 pooled together
- Age in class 50 – ≤60 ; >60 – ≤70 years ; >70 – ≤80 years ; > 80 years]
- Gender (Male/Female)
- Cardiological symptomatology (Yes/No, where patient with a cardiological symptomatology are defined as patient with a least one cardiological manifestation (point 7 in 0)
- High Creatinine, high BNP and high NTproBNP (See Section 6.3, § 8)

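### Three numeric limits in the SAP's cardiological-manifestations flag contradict eligibility or their own label, and a flag made only of signs and findings is reused as symptomatology

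*SAP*

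**What the plan says.** SAP 6.3, item 7, sets an any-one-of rule: "Patients with cardiological signs will be defined as patients with at least one of the following criteria fulfilled". The table below it has 24 rows. Maximal wall thickness (MWT) counts when it is "< 15 mm or > 100 mm". Aortic valve area (AVA) counts when it is below 0.2 or above 3 cm². Septum and posterior wall each count below 3 or above 50 mm, and LV mass index below 40 or above 160 g/m².

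The population is defined the other way round. SAP 5.1 says "Full Analysis Set 1 (FAS1) includes all patients who meet eligibility (inclusion/exclusion) criteria" and a scan, and FAS2 and FAS3 are subsets of it. Inclusion criterion d (SAP 2.1, Protocol 9.2.5) begins "Left ventricular hypertrophy (LVH) defined as end-diastolic LV maximum wall thickness (MWT" and sets a minimum of 15 mm. Exclusion criterion b in the SAP reads "Severe aortic stenosis defined as aortic valve area (AVA) < 1.0 cm" (squared), and the protocol's criterion is the same. The variables table in Protocol 9.3, however, records severe stenosis at inclusion as "Maximal aortic velocity >4 m/s or Mean gradient >40 mmHg".

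SAP 6.4 then reuses the flag: "patient with a cardiological symptomatology are defined as patient with a least one cardiological manifestation". SAP 8.1 runs the 6.4 covariates through the univariate logistic models, from which they can pass to the multivariate model. Protocol 9.7 and the abstract stratify by cardiac symptomatology. SAP 11.1 closes by leaving abnormal values of all quantitative variables to later medical advice.

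**The concern.** An any-one-of flag is only as sound as its weakest criterion, because a single value makes the patient positive. If a criterion cannot be met by an eligible patient whose records agree, it turns data errors into manifestations. If a criterion runs against its own row, it counts the opposite of the intended finding.

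The flag is a named secondary endpoint, tabulated in SAP 8.2 for FAS2, FAS3, FAS 3.1 (also split by ATTRv and ATTRwt) and FAS 3.2. Its second use matters separately: a reader who sees an odds ratio for cardiological symptomatology will take it as a statement about symptoms.

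**Working it through.** The documents give no figure for this flag, so there is none to reproduce. The check is a count and a side-by-side reading. A limb here means one one-sided numeric cut-off.

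**1. Count (SAP 6.3, item 7).** There are 24 rows: 13 categorical and 11 numeric. Nine numeric rows are two-sided (PR, QRS, Sokolow, LV end-diastolic diameter, MWT, septum, posterior wall, LV mass index, AVA) and two are one-sided (aortic velocity, mean gradient). Limbs: 9 × 2 + 2 = 20.

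**2. Limbs against the rest of the plan.**

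| Limb | Compared with | Result |
|---|---|---|
| MWT < 15 mm | Inclusion d: at least 15 mm | Contradicts eligibility |
| AVA < 0.2 cm² | Exclusion b: below 1.0 cm² excluded | Contradicts eligibility |
| AVA > 3 cm² | Its own row, which names stenosis | Runs opposite to its label |
| Septum < 3 mm; posterior wall < 3 mm; LV mass index < 40 g/m² | Cohort selected for hypertrophy | Points away from it; contradicts no text |
| Velocity > 5 m/s; gradient > 70 mmHg | Protocol 9.3: > 4 m/s or > 40 mmHg | Conflict only if 9.3 governs exclusion |

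Contradicting eligibility: 2 of 20. Wrong on the documents' own terms: 2 + 1 = 3 of 20 (15%).

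**3. When the MWT and AVA limbs can fire.** Protocol 9.3 lists maximal wall thickness at inclusion and MWT again under clinical evaluation. With eligibility applied as written, MWT < 15 mm can be met in FAS1 only if the two records disagree. For AVA, an eligible patient with concordant data has at least 1.0 cm², so the only limb within reach is > 3 cm². An area from 0.2 to just under 1.0 cm², which the exclusion calls severe, would not be flagged at all.

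**4. The three hypertrophy-opposed limbs.** With MWT of at least 15 mm, a septum or posterior wall below 3 mm needs a gap of more than 15 − 3 = 12 mm, or more than 15 / 3 = 5-fold, between segments. That is extreme but not excluded, since MWT is a maximum over segments.

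**5. Symptoms.** All 24 rows are rhythm, device, ECG, MRI or echocardiographic findings: 0 of 24 is a symptom. The protocol's strata are age, gender and cardiac symptomatology. All three reappear in SAP 6.4, the last defined by this flag. NYHA class is collected (Protocol 9.3) but is not in the flag.

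**6. Scale.** If *k* patients are positive solely through a faulty limb, the reported prevalence rises by *k*/*n*. No document gives *k*. For *n*, assume the protocol's 10% prevalence: 10% of 1,500 = 150, so 1/150 = 0.67 percentage points per patient; 10% of 1,000 = 100, so 1.0 point. Denominators in the other reported sets will differ.

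**The case against.** The best case for leaving the table alone has five parts.

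- **The contradictory limbs should be silent on clean data.** Protocol 9.6 plans a data validation document and a clarification process for discrepancies, and 9.8.2 has monitors check the CRF against source. This limits the impact. It does not remove the limbs: a discordance that survives cleaning would still be counted as a manifestation.
- **A limb changes the flag only when no other criterion is positive.** With 13 categorical items such as late gadolinium enhancement, pacemaker or bundle branch block, that may be uncommon. This stands, and it is why no net effect is claimed.
- **Two-sided limits are used elsewhere.** SAP 6.3, item 8, flags low creatinine and high haemoglobin, and item 7 asks for signs, not for evidence of hypertrophy. This stands for septum, posterior wall and LV mass index, where whether the low limb belongs is a clinical judgement. It does not rescue AVA > 3 cm² under a stenosis label.
- **SAP 11.1 leaves abnormal values to medical advice.** It does, for all quantitative variables. But item 7 already fixes numbers, and nothing says which governs; a programmer would code item 7.
- **SAP 6.4 states its definition openly, and the protocol never defines cardiac symptomatology.** Both are true. The label still says symptoms where item 7 itself says signs.

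A reader might go further and infer that 6 or 8 of the 20 limbs are errors. The documents do not support this: three of the six are only implausible, and the velocity and gradient limbs depend on an unresolved definition. A reader might also fault the upper wall limits (100 against 50 mm), the PR limit or the Sokolow limit. MWT and the named walls are separate variables, the PR classes in SAP 11.1 are descriptive bins, and no passage defines low voltage by Sokolow index, so no error is shown there.

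**Conclusion.** The point holds in a limited form. Two limbs contradict the eligibility that defines FAS1 to FAS3, one contradicts its own label, and a flag with no symptom in it carries the name of the protocol's symptom stratum. The first two findings assume that exclusion b is applied as an area rule, as both eligibility lists state. That SAP 6.4 stands in for the protocol's stratum is read from the matching lists; the SAP does not say so.

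The consequence is a secondary endpoint that can count discordant records or a large valve area as disease manifestations, and a covariate open to misreading. A material bias in the reported prevalence might be inferred, but the documents give no number of such patients, so none can be claimed. The primary endpoint is unaffected, SAP 4.2 calls all tests exploratory, and the single CRF variables are still described and modelled. The SAP should be corrected, but the study's main result is not at risk.

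**What to change.** - **Flag.** Remove MWT < 15 mm, AVA < 0.2 cm² and AVA > 3 cm² from item 7, and handle such values as discrepancies under the existing process in Protocol 9.6. Keep the 13 categorical items.
- **Other numeric limits.** Put them, including septum < 3 mm, posterior wall < 3 mm and LV mass index < 40 g/m², through the medical review in SAP 11.1. State before database lock that its result replaces the limits in item 7. No cut-off is proposed here.
- **Stenosis.** Reconcile the area-based exclusion ("Severe aortic stenosis defined as aortic valve area (AVA) <1.0 cm", squared, in the protocol) with the velocity and gradient definition in Protocol 9.3 before keeping the velocity and gradient limbs.
- **Covariate.** Rename it cardiological signs in SAP 6.4. Report the protocol's symptomatology stratum from a symptom variable already collected. NYHA class is one candidate; the documents do not prescribe it. The sponsor should fix the grouping in advance and report missingness, because assessments are collected only if performed and SAP 7 imputes nothing.

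Cost: one SAP table and one label revised, one flag re-derived and a short clinical review, with no new variables to collect. NYHA class may be missing for some patients. Queries to sites may also come late, since data collection was planned to end in June 2022 and SAP version 2 is dated 6 July 2022.
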